5.5.7 Surgery

Any surgery conducted during the study period must be justified and necessary. The interval between the surgery and study treatment must not affect the recovery of the wound as much as possible and the investigation on hemorrhage of unknown cause. An interruption of study treatment 1 week before the surgery is recommended. Re-administration of the drugs after surgery will be determined on the basis of clinical assessment of wound healing and postoperative recovery.

5.5.8 Supportive care

Palliative and supportive care for disease-related symptoms should be based on the investigator's judgment and relevant guidelines (e.g., "American Society of Clinical Oncology Clinical Practice Guideline").

Subjects should be given optimal supportive care during the treatment.

It is not recommended to enroll subjects with uncontrolled cancer pain. Subjects requiring analgesics must have a stable analgesic regimen before enrollment. Palliative radiotherapy for symptomatic lesions (such as bone metastasis or perineural invasion) should be completed at least 2 weeks before enrollment. Local treatment should be considered before the start of study treatment, if appropriate, for asymptomatic metastatic lesions where further growth may result in dysfunction or intractable pain (e.g., epidural metastasis without spinal cord compression).

RANKL inhibitors (receptor activator of nuclear factor κ B ligand inhibitor such as denosumab) are prohibited. Subjects with uncontrolled hypercalcemia (calcium ion > 1.5 mmol/L or calcium > 12 mg/dL or corrected serum calcium $>$ ULN), or subjects who need to continue treatment with bisphosphonates or denosumab for symptomatic hypercalcemia are not recommended to be enrolled. Patients who receive bisphosphonate therapy only to prevent skeletal-related events and have no history of clinically significant hypercalcemia may be enrolled. Patients receiving denosumab prior to enrollment must agree to replace denosumab with a bisphosphonate after entering the study.

Existing hormone replacement therapies are permitted. For example, subjects receiving treatment with a GnRH agonist can be enrolled in this study provided that the GnRH agonist has been well-tolerated for at least 3 months prior to enrollment. Likewise, patients with a history of autoimmune-mediated hypothyroidism who are receiving stable doses of thyroid hormone replacement therapy may be enrolled in this study. Patients with type 1 diabetes who are receiving on stable insulin therapy and have properly controlled blood glucose can be enrolled.

5.6 Recommended Symptomatic Treatment for Common Adverse Drug Reactions Related to SHR-1210

5.6.1 Safety management rules for immuno-oncological medications

AEs caused by immuno-oncology (I-O) medications are different from those of other anti-cancer drugs, especially in terms of severity and duration. SHR-1210 is one such drug, and therefore, early identification and management of adverse events is required to reduce the incidence of severe toxicities. The safety management procedures of similar approved drugs provide references to assist the investigator in assessing and dealing with adverse events involving the following systems: GI tract, kidneys, lungs, liver, endocrine, skin, and nervous system. Safety management rules for immuno-oncology drugs are presented in [Appendix 4 Management Principles for Immune Related Adverse Events](#).

5.6.2 Infusion reactions

During the course of this study, the investigator should pay close attention to potential infusion and/or allergic reactions, especially acute immune-mediated adverse reactions (including cytokine storms).

SHR-1210 is a fully humanized monoclonal antibody with little potential for infusion or allergic reactions, and thus, in general, no prophylactic medications are required prior to SHR-1210 infusion. Based on published relevant information, an allergic reaction/event is most likely to occur within 24 h after infusion. If an allergic reaction/event occurs, the infusion should be slowed or interrupted based on the subject's condition, and supportive treatment should be given. In addition, prophylactics should be given before further administration. Possible allergic reactions include fever, chills, shiver, headache, rash, arthralgia, hypotension/hypertension, and bronchospasm.

Management of allergic reactions should be based on the medical practice and guidelines of the study center. The treatment recommendations for infusion reaction are shown below ([Table 10](#)) for reference.

Table 10. Treatment recommendations for infusion reaction related to SHR-1210

CTCAE Grade	Clinical Symptoms	Recommended Management	SHR-1210 Treatment
Grade 1	Mild and transient reactions	Bedside observation and close monitoring until recovery. Pre-dose prophylactics are recommended for subsequent administrations: 50 mg of diphenhydramine or equivalent, and/or 325–1000 mg of acetaminophen can be given at least 30 min before the administration of SHR-1210.	Continued use

CTCAE Grade	Clinical Symptoms	Recommended Management	SHR-1210 Treatment
Grade 2	Moderate reactions requiring treatment or interruption; rapidly resolve after symptomatic treatment (such as antihistamines, non-steroidal antiphlogistics, anesthetics, bronchodilators, intravenous fluids, etc.)	Intravenous administration of normal saline, 50 mg of diphenhydramine IV or equivalent and/or 325-1000 mg of acetaminophen; bedside observation and close monitoring should be given until recovery. Corticosteroids or bronchodilators can be considered based on clinical needs; The amount of study drug infused should be recorded in the original medical record; Pre-dose prophylactics are recommended for subsequent administrations: 50 mg of diphenhydramine or equivalent, and/or 325-1000 mg of acetaminophen can be given at least 30 min before the administration of SHR-1210. Corticosteroids (equivalent to 25 mg of hydrocortisone) can be used when necessary.	Interrupt. Re-administer at 50% of the initial rate after symptoms resolve. Restore the original infusion rate if no complications occur within 30 minutes. Closely monitor. If the symptoms recur, no more infusion shall be given.
Grade \geq 3	Grade 3: Severe reaction without rapid recovery with treatment and/or interruption; or symptoms recur after alleviation; or the subject develops sequelae that requires hospitalization. Grade 4: Life-threatening.	Immediately discontinue SHR-1210; Administer normal saline by intravenous infusion. Bronchodilators are recommended. Subcutaneous injection of 0.2-1 mg of 1:1000 adrenaline solution or slow intravenous infusion of 0.1-0.25 mg of 1:10,000 adrenaline solution is recommended. Intravenous infusion of diphenhydramine 50 mg and methylprednisolone 100 mg (or equivalent dose) can be given if necessary. Medical practices and guidelines for treating allergic reactions at the study center are followed. Bedside observation and close monitoring until recovery.	Discontinuation

6 STUDY PROCEDURES

6.1 Screening Period

The screening period is the time from the signing of the informed consent form until the start of study treatment or screen failure.

Subjects must sign the informed consent form before undergoing screening procedures for this study. Data from laboratory tests and imaging evaluation performed prior to informed consent for routine clinical practice may be used if they are within the specified window period.

Unless otherwise stated, the following screening procedures should be completed within 28 days prior to the start of the study treatment.

- Obtain informed consent form signed by the subject.
- Collection of demographics: gender, date of birth, ethnicity, height, and weight.

- Collection of adverse events: Collect adverse events starting from the signing of ICF.
- Tumor diagnosis: date of pathological diagnosis, pathologic grade, pathologic stage (TNM), clinical stage, site of metastatic lesion, time to disease progression or recurrence from the last treatment.
- History of cancer treatment
 - ✓ History of tumor surgery: surgery, date;
 - ✓ History of radiotherapy: site, dose, and start and end dates.
 - ✓ History of neoadjuvant chemotherapy: chemotherapy regimen, cycles, and start and end dates;
 - ✓ History of adjuvant chemotherapy: chemotherapy regimen, cycles, and start and end dates;
 - ✓ History of concurrent disease, past medications, and medication allergies;
- Virology: HBsAg, HBsAb, HBeAg, HBeAb, HBcAb, HBV DNA (if the Hepatitis B five items test indicates HBV infection [HBsAg positive] or if the subjects have a history of HBV infection, HBV DNA quantification should be performed), HCV-Ab (if the result is positive, HCV RNA quantification should be performed), and HIV-Ab.
- Imaging examinations: CT or MRI of the chest, abdomen, and pelvic cavity. Brain MRI (if MRI is contraindicated, CT scan can be used instead) is required for suspected or confirmed brain metastases. Bone scan is performed only when clinically indicated and must be performed within 42 days prior to the first dose. At screening, tumor evaluations up to 4 weeks before the first dose of study treatment and before the signing of the informed consent may be used as long as they meet relevant requirements.
- Concomitant medications/concomitant treatments: Concomitant medications/concomitant treatments within 30 days prior to the first dose of the study drug are documented.

The following screening procedures should be completed within 7 days prior to the start of the study treatment. A pregnancy test should be completed within 72 hours prior to the start of the study treatment.

- ECOG PS.
- Vital signs: pulse, respiratory rate, body temperature, and blood pressure.

- Comprehensive physical examination: general condition, head and face, skin, lymph nodes, eyes, ears, nose and throat, oral cavity, respiratory system, cardiovascular system, abdomen, reproductive-urinary system, musculoskeletal system, nervous system, mental state, etc.;
- Hematology: Red blood cell count (RBC), hemoglobin (Hb), platelet count (PLT), white blood cell count (WBC), absolute neutrophil count (ANC), and lymphocyte count.
- Urinalysis: WBC, RBC, and urine protein. If urine protein is $\geq 2+$, then a quantitative 24-h urine protein test should be added.
- Fecal occult blood (OB) test: Fecal occult blood test is performed within 7 days prior to the first dose (if the fecal occult blood is positive, the test should be performed again. If the result is still positive, gastrointestinal endoscopy should be performed), on Day 1 of every two cycles, at the end of treatment/upon withdrawal, and upon the first visit during the safety follow-up period.
- Blood biochemistry: Alanine transaminase (ALT), aspartate aminotransferase (AST), gamma-glutamyl transferase (γ -GT), total bilirubin (TBIL), direct bilirubin (DBIL), alkaline phosphatase (AKP), blood urea nitrogen (BUN, preferred) or urea, total protein (TP), albumin (ALB), creatinine (Cr), blood glucose (GLU), K^+ , Na^+ , Ca^{2+} , Mg^{2+} and Cl^- .
- Thyroid function: Including serum thyroid stimulating hormone (TSH), free triiodothyronine (FT3), and free thyroxine (FT4). If FT3 and FT4 cannot be obtained, T3 and T4 are allowed for substitution;
- Coagulation function: Activated partial thromboplastin time (APTT), prothrombin time (PT), thrombin time (TT), fibrinogen (FIB), and international normalized ratio (INR).
- 12-Lead ECG: Attention should be paid to QT, QTc, and PR-intervals. The investigator may decide to add other investigations if the results are abnormal.
- Echocardiography: Including left ventricular ejection fraction (LVEF) assessment. Echocardiography is performed once within 7 days before the enrollment. After that, echocardiography is performed if clinically indicated and at the end of treatment/upon withdrawal.
- Pregnancy test (serum pregnancy test will be performed for women of childbearing potential).

6.2 Treatment Period/Follow-Up

The treatment period starts from the subject's first dose. The first dose of the study drugs should be given as close as possible to the time of completing the screening examinations and confirming the subjects' eligibility for the study. Each treatment cycle lasts for 21 days.

All examinations and evaluations (except for imaging evaluations) should be completed within 3 days pre-administration. There is no need to repeat the laboratory tests (hematology, urinalysis, blood biochemistry, coagulation function test, and thyroid function test) and electrocardiography on Day 1 of Cycle 1, if such tests have already been performed at the baseline within 7 days before the first dose.

- ◆ For subjects receiving the SHR-1210 + apatinib treatment for the first time, blood samples should be collected for PK and immunogenicity testing. The specific procedures can be found in the schedule of activities or section 3.1 "Pharmacokinetic and Immunogenicity Studies" in the protocol.
- ◆ The following evaluations should be completed before the drug administration in each cycle:
 - ECOG PS
 - Vital signs
 - Physical examination: Specific physical examination is performed if clinically indicated.
 - Hematology
 - Clinical chemistry
 - Coagulation function
 - 12-Lead ECG
 - Collection of AEs
 - Documentation of concomitant medications/concomitant treatments
- ◆ The following evaluations should be completed every 2 cycles prior to administration:
 - Urinalysis
 - Thyroid function
 - Fecal occult blood

- ◆ Imaging examination: Imaging examination is performed once every 2 cycles (6 weeks ± 7 days) in the first 12 months (the first 16 cycles), then once every 3 cycles (9 weeks ± 7 days). Imaging examination should be also performed if new lesions are suspected. Imaging examination should be performed when subjects withdraw from the study for any reason (the imaging examination does not need to be repeated if the time from the last examination is no more than 4 weeks). Imaging conditions should be the same as those at baseline (including slice thickness and contrast agent). The time window for imaging examination is ± 7 days. Unscheduled imaging examination may be performed if PD is suspected (for example, worsening of symptoms). The date of imaging examination is calculated by the calendar day and will not be adjusted due to dose delays.

Subjects with CR and PR should receive repeated imaging examination once to confirm the efficacy. Repeated tumor imaging should be performed at least 4 weeks after the initial response (4 weeks after the initial response or the next scheduled imaging evaluation). If the subject's imaging evaluation time is less than 4 weeks to the next scheduled imaging time, the next scheduled imaging evaluation is not required, and the imaging evaluation can be resumed at subsequent scheduled time point.

6.3 End of Treatment/Withdrawal Visit

If relevant assessments and examinations have not been performed within 7 days before the last dose, the following procedures should be followed:

- ECOG PS
- Vital signs
- Comprehensive physical examination: general condition, head and face, skin, lymph nodes, eyes, ears, nose and throat, oral cavity, respiratory system, cardiovascular system, abdomen, reproductive-urinary system, musculoskeletal system, nervous system, mental state, etc.;
- Hematology
- Urinalysis
- Fecal occult blood
- Clinical chemistry
- Coagulation function
- Thyroid function

- ECG
- Imaging examination: Imaging examination should be performed in time (\pm 4 weeks; there is no need to repeat the imaging examination upon withdrawal if the time from the previous examination to the discontinuation is less than 4 weeks). Subjects who discontinue treatment for reasons other than radiographically confirmed PD must also undergo imaging examination at the frequency specified in the protocol until documented of confirmed PD, start of a new anti-tumor treatment, or death.
- Collection of AEs
- Documentation of concomitant medications/concomitant treatments

6.4 Follow-up period

6.4.1 Safety follow-up period

Safety follow-up starts from the last dose of study treatment. The follow-up is performed once every 30 days (\pm 7 days) until 90 days after the last dose.

The first safety follow-up (30 days \pm 7 days) is carried out at the study center where the evaluations specified in the protocol are completed. The second (60 days \pm 7 days) and the third (90 days \pm 7 days) follow-up are made via telephone calls. The information on survival, concomitant medications/concomitant treatments and AEs are collected.

- ◆ During the first safety follow-up (30 ± 7 days), the subjects should receive the following evaluations at the study center (if the subject has started a new anti-tumor treatment before the first safety follow-up, then the follow-up should be completed before starting the new anti-tumor treatment):
 - ECOG PS
 - Vital signs
 - Physical examination: Specific physical examination is performed if clinically indicated.
 - Hematology
 - Urinalysis
 - Fecal occult blood
 - Clinical chemistry
 - Thyroid function

- Coagulation function
 - ECG
 - Collection of AEs
 - Documentation of concomitant medications/concomitant treatments
- ◆ For the second (60 days after the last dose) and the third safety follow-ups (90 days after the last dose), the subjects' survival information and AEs can be collected via telephone calls.
- ◆ Imaging examination: Subjects without radiographically confirmed disease progression should receive imaging examination at the same frequency as that during the treatment period.

6.4.2 Survival follow-up

The survival follow-up period starts after the end of the safety follow-up period. The survival follow-up period ends upon the subject's death, lost to follow-up, withdrawal of informed consent, or study termination by sponsor. During this period, an effective follow-up such as telephone follow-up is conducted once every month to collect information on subject survival and subsequent treatments (if the subject has started a new anti-cancer treatment, the therapeutic regimen and the start and end time should be recorded).

For subjects who show no evidence of radiographic progression, imaging evaluation will be continued at the same frequency of efficacy evaluations specified in the protocol, until progressive disease, death, lost to follow-up, withdrawal of informed consent, start of other anti-cancer treatment, or study termination by the sponsor. Evidence of radiographic progression should be collected as much as possible for these subjects.

6.5 Unscheduled Visit

The following shall be documented during unscheduled visits when subjects develop AEs during the study:

- Concomitant medications/treatments;
- Adverse events;
- All relevant examinations (including imaging evaluations, if any).

7 STUDY EVALUATION

7.1 Efficacy Evaluation

7.1.1 Efficacy endpoints

The primary efficacy endpoint of this study is objective response rate (ORR).

Objective response rate (ORR): the proportion of treated subjects with a best overall response (BOR) of complete response (CR) or partial response (PR) as per RECIST 1.1 criteria. If the subject achieves CR or PR, conformation should be done at least 4 weeks (28 days) after the first evaluation. Best overall response refers to the best response assessed by the investigator, or the best response from the date of enrollment to the first documentation of progression as per RECIST 1.1 or to the start of a new anti-tumor treatment (whichever comes first). For subjects without documented progression or new anti-cancer treatment, BOR will be determined based on all response evaluations. For subjects who continue SHR-1210 treatment beyond progression, the best overall response should be based on the efficacy assessment at the time of first documented progression as per RECIST 1.1. Efficacy evaluation should be performed once every 2 cycles (6 weeks \pm 7 days) in the first 12 months (first 16 cycles) from the study treatment. Then it is performed once every 3 cycles (9 weeks \pm 7 days) after 12 months until PD (or discontinuation of the study treatment for subjects continuing the SHR-1210 after PD), lost to follow-up, withdrawal of informed consent or death.

Secondary efficacy endpoints include progression free survival (PFS), duration of response (DoR) and disease control rate (DCR).

Progression-free survival (PFS): The time between the date of enrollment and the first documented tumor progression (as per RECIST 1.1 criteria, regardless of whether treatment is continued), or death due to any cause, whichever occurs first. When determining PFS, clinical exacerbations without definite evidence of progressive disease (as per RECIST 1.1) is not considered progressive disease. For subjects who die without any prior reports of progression, the date of death is considered the date of progression. Subjects without progressive disease or death will be censored on the date of their last evaluable tumor assessment. Subjects without tumor assessments during the study or death will be censored on their date of enrollment. Subjects who discontinue the treatment for reasons other than progressive disease (no subsequent tumor assessments) will be censored on their date of study discontinuation. For subjects who have not previously reported progressive disease but have initiated subsequent anti-tumor therapy, they will be censored on the date of their last evaluable tumor evaluation before starting the subsequent anti-tumor therapy, or they will be censored when starting the subsequent anti-tumor therapy. When subjects are not censored on the date of study discontinuation or the date of starting new anti-tumor treatment, the

scheduled sensitivity analysis will confirm PFS based only on the time of radiologically confirmed progression events. The occurrence of a new tumor will not be considered a progressive disease and is not censored.

Disease control rate (DCR): the proportion of subjects with a best overall response of complete response (CR), partial response (PR), or stable disease (SD) as per RECIST 1.1 criteria. If the subject achieves CR or PR, confirmation should be done at least 4 weeks (28 days) after the first evaluation. Best overall response refers to the best response assessed by the investigator, or the best response from the date of enrollment to the first documentation of progression as per RECIST 1.1 or to the start of a new anti-tumor treatment (whichever comes first). For subjects without documented progression or new anti-cancer treatment, BOR will be determined based on all response evaluations. For subjects who continue SHR-1210 treatment beyond progression, the best overall response should be based on the efficacy assessment at the time of first documented progression as per RECIST 1.1.

Duration of response (DoR) is defined as the period of time from the first documented tumor response (as per RECIST 1.1) to the first documented objective progression (as per RECIST 1.1) or death of any cause. Subjects without progressive disease or death will be censored on the date of their last tumor assessment. Subjects who start any subsequent anti-tumor therapy (excluding palliative radiotherapy of non-target bone lesions or central nervous system lesions during the study treatment) without previously reported progressive disease will be censored on the date of last tumor assessment prior to the start of new anti-tumor treatment, or on the date of starting the new anti-tumor treatment.

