## 2 PROTOCOL AMENDMENT

Added overall survival (OS), time to objective response (TTOR), and subgroup analysis as exploratory efficacy analysis to provide guidance for subsequent phase III clinical studies

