**Table 3. Date of progressive disease, death, or censoring**

		No	Yes
1.	Does the subject have a baseline objective tumor assessment?	Censoring The date of censoring is the date of randomization	Skip to 2
2.	Are new anti-cancer drugs used before progressive disease or death?	Skip to 3	Censoring The date of censoring is the date of the last objective tumor assessment before the use of the new anti-cancer drug
3.	Has the subject experienced progressive disease?	Skip to 5	Skip to 4
4.	Is the progressive disease of the subject recorded after an unacceptably long time interval (the response evaluation is missing by > 2 times, i.e., 98 days)?	Progressive disease The date of progression is the date of earliest recorded progressive disease	Censoring The date of censoring is the date of the last objective tumor assessment before the long-term lost to follow-up
5.	Is the subject dead?	Censoring The date of censoring is the date of the last objective tumor assessment	Skip to 6
6.	Is the death of the subject recorded after an unacceptably long time interval (the response evaluation is missing by > 2 times, i.e., 98 days)?	Progressive disease The date of progression is the date of death	Censoring The date of censoring is the date of the last objective tumor assessment before the long-term lost to follow-up

The time of PFS is based on the time of the imaging examination rather than the time of the visit. The RECIST imaging examination time (targeted lesion, non-targeted lesion, and new lesion) for a special visit may be different, and the following rules apply:

- The date of progression will be based on the earliest date leading to progression.
- The date of censoring will be based on the last date of objective tumor assessment.

Survival curves will be plotted using the Kaplan-Meier method and the 95% CI for median time will be calculated using the Brookmeyer-Crowley method.

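### The SAP omits the protocol's scheduled PFS sensitivity analysis without saying so, leaving PFS on a single censoring scheme that may be informative

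*Protocol*

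**What the plan says.** **Protocol 7.1.1** gives main PFS rules that include censoring at study discontinuation (when no later scans exist) and at subsequent anti-tumor therapy. It also says that "clinical exacerbations without definite evidence of progressive disease (as per RECIST 1.1) is not considered progressive disease". A further sentence opens "When subjects are not censored on the date of study discontinuation or the date of starting new anti-tumor treatment, the" and continues "scheduled sensitivity analysis will confirm PFS based only on the time of radiologically confirmed progression events". Protocol 8.4.2 does not repeat this commitment, so 7.1.1 is its only source.

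**SAP 11.5.2.3** has one scheme, Table 3. For a subject who starts a new anti-cancer drug before progression or death: "The date of censoring is the date of the last objective tumor assessment before the use of the new anti-cancer drug". Progression or death after a long gap is also censored, the gap being described as "the response evaluation is missing by > 2 times, i.e., 98 days". The only PFS outputs are then: "Survival curves will be plotted using the Kaplan-Meier method and the 95% CI for median time will be calculated using the Brookmeyer-Crowley method".

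**SAP section 2** lists differences from the protocol: "Added overall survival (OS), time to objective response (TTOR), and subgroup analysis as exploratory efficacy analysis". It does not mention that a PFS analysis was dropped.

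**The concern.** A check that the protocol calls scheduled would not be produced by anyone following the SAP, and nothing records a decision to drop it.

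The check matters because of how three rules combine. Deterioration without RECIST progression is not an event. Protocol 4.6 and 7.1.2 foresee treatment being stopped for general deterioration without objective progression. Table 3 then censors the patient at the last scan before any new drug. Kaplan-Meier estimation assumes that censored patients have the same outlook as those still at risk. Patients who switch because they are getting worse would not, and the estimated PFS would be too long. The trial is open-label with investigator assessment, so the decision to switch is made knowing the treatment. SAP section 2 says the added exploratory analyses are meant to guide phase III, and those include PFS subgroups built on the same scheme.

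**Working it through.** **1. Is the analysis anywhere in the SAP?** These are the places that deal with PFS or repeat analyses:

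| SAP section | Content | Alternative PFS censoring? |
|---|---|---|
| 9.1 | PFS definition | No |
| 10.1 | Missing tumor assessments | No |
| 11.5 | Efficacy on the FAS, PFS by cohort | No |
| 11.5.1.2 | Repeats ORR on FAS, PPS and ES | No (ORR only) |
| 11.5.2.3, Table 3 | Main PFS scheme | No |
| 11.5.3.3 | PFS subgroups on the FAS | No |

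It is absent. Protocol 8.1 allows the SAP to revise protocol content but says that changes to main or key factors, with endpoint analysis as an example, go back into the protocol. On either view the two documents now disagree.

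**2. What does Table 3 do to a switcher?** Row 2, on new drugs, comes before the rows on progression and death. A subject with a new drug is censored there, so a later progression or death never enters. Protocol 6.4.2 follows survival monthly, so those deaths are recorded but unused for PFS.

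**3. The gap rule.** 98 days reproduces as 2 × (42 + 7). After month 12 scans are 63 days apart, so one missed scan leaves 2 × 63 = 126 days, already over 98. Late events can therefore be censored after a single missed scan.

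**4. Size, as illustration only.** The plan states no PFS figure to reproduce. Assumptions:
- True median PFS of 6.6 months, from the first-line pembrolizumab-plus-chemotherapy cohort cited in protocol 1.2; exponential times; protocol scan schedule.
- Share f who switch before progression: not in the documents; 10% to 20% assumed.

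With nobody censored, the last scheduled scan by 12 months is day 8 × 42 = 336, or 336/30.4375 = 11.04 months. Recorded 12-month PFS is then 2^(−11.04/6.6) = 31.4%. Simulation with 400,000 subjects gives 31.5%.

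Under the Table 3 switching rule, simulated:

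| When switching happens | f | 12-month PFS | Excess (points) |
|---|---|---|---|
| Within 2 months before progression | 10% | 34.7% | 34.7 − 31.5 = 3.2 |
| | 15% | 36.5% | 36.5 − 31.5 = 5.0 |
| | 20% | 38.5% | 38.5 − 31.5 = 7.0 |
| Spread over the time before progression | 10% to 20% | 33.4% to 35.9% | 2.0 to 4.5 (against 31.4%) |
| Independent of prognosis | any | median unchanged at 6.9 months | essentially none |

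For the median, take the extreme case in which every switcher is censored at the moment of progression. The apparent hazard is (1 − f)λ, so apparent median = true median/(1 − f):
- 6.6 months becomes 6.6/0.9 = 7.3 or 6.6/0.8 = 8.3.
- 4 months becomes 4.4 or 5.0.
- 9 months becomes 10.0 or 11.3.

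On the scan grid the median moves from 6.9 to 8.3 months at both 10% and 20%. That is one 6-week step (42/30.4375 = 1.4 months), so landmark rates measure the effect better.

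**The case against.** **Restoring the protocol's analysis word for word would barely test the bias.** This stands. Scheduled imaging ends at new anti-tumor treatment (protocol 3, 6.4.2, 7.1.2), so an uncensored switcher usually has no later scan. Taken literally, counting only radiological progression would also drop deaths that Table 3 counts, which tends to lengthen PFS. A reader might infer that copying the protocol sentence into the SAP is enough; the imaging rules show that it is not.

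**The protocol sentence is ambiguous.** It speaks of censoring on the date of discontinuation or of new treatment, and Table 3 uses neither date. That is fair, but Table 3 still censors the switcher, only earlier. Even on the narrow reading, the analysis of radiological events is missing.

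**The protocol has safeguards.** Imaging is called for when progression is suspected and at withdrawal unless done within 4 weeks (protocol 6.2, 7.1.2). Some deteriorating patients will have RECIST progression recorded before a switch. The simulation ignores these scans and so may overstate the effect.

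**The figures rest on assumptions.** Also fair. The 6.6 months comes from 25 subjects on a different regimen and does not represent cohort 2. Around 31.5%, a 95% interval is about ±1.96 × √(0.315 × 0.685/43) = ±14 points with 43 subjects and ±12 with 55. Sampling error therefore exceeds the illustrated shift, though it does not remove a systematic one.

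**The consequences are limited.** PFS has no hypothesis or power, decisions rest on ORR, and OS in SAP 11.5.3.1 is not censored at new therapy. This limits the importance of the point but does not explain the omission.

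**Conclusion.** The omission is established from the text: the protocol schedules a PFS sensitivity analysis, the SAP has none, and the SAP does not declare the removal. It should be put right, but it does not touch the ORR decision.

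The bias is plausible, not shown. A reader might infer that Table 3 censoring is informative and does lengthen PFS. The documents do not support that as fact: they give neither how many patients switch before progression nor why. Under the stated assumptions the excess in 12-month PFS is about 2 to 7 points, and essentially none if switching is unrelated to prognosis. Nor should the step from 6.9 to 8.3 months be read as the size of the bias, since it reflects the scan grid. It would also be wrong to say that PFS rests on one censoring rule: Table 3 is one scheme with several rules, of which those for new therapy and long gaps matter here.

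**What to change.** Add to SAP 11.5.2.3, by cohort:

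- **(a)** PFS ignoring new therapy and the 98-day gap rule, counting every recorded RECIST progression and every death. State explicitly that deaths count.
- **(b)** PFS with the start of new anti-cancer therapy counted as an event.

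Both are needed. Post-switch scans in (a) will be sparse, so some switchers will have their event dated at death, later than an unseen progression. Analysis (b) needs no post-switch scans, but it counts a switch as failure even in a patient who would have stayed progression-free. In the simulation with switching at the moment of progression, (b) returned the uncensored median of 6.9 months at every switching share.

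Report medians and landmark rates from both beside the Table 3 result, tabulate censoring reasons by cohort, and list the departure from protocol 7.1.1 in SAP section 2. If the sponsor prefers not to run a sensitivity analysis, it should amend the protocol and justify the removal.

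The cost is one or two extra Kaplan-Meier tables per cohort. No new data collection is needed: survival and the start of subsequent treatment are already collected monthly under protocol 6.4.2.
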